### Interim Analysis and Stopping Rules

Interim analyses will be conducted to evaluate safety endpoints but will not be conducted to evaluate conditional power (futility) or to assess efficacy.

Safety will be evaluated by examining group differences in death and serious adverse events semi-annually in conjunction with scheduled DSMB meetings to evaluate the safety of the study intervention, and the associated risk-to-potential benefit ratio. The Principal Investigators will address study efficacy only at the end-of-study, and thus will not consider terminating the trial early on the basis of conditional power (futility) or evidence of efficacy. This is because firm evidence will be required to change current clinical practice, and because trials that have stopped early for efficacy often report implausibly large effect sizes (and therefore should be considered with skepticism). At the conclusion of each DSMB meeting, the Board should take into account the statistical evidence as well as practical and clinical considerations to make one of the following recommendations based on safety:

- a. Suspend enrollment due to safety concerns secondary to study intervention including:
  1. A difference in all-cause mortality between patients randomized to the deprescribing intervention versus usual care such that the DSMB deems the difference to be study-related and excessive.
  2. A difference in drug related SAEs between patients randomized to the deprescribing intervention versus usual care such that the DSMB deems the difference to be study-related and excessive.
- b. Continue Enrollment

### Outcomes

**Hypotheses 1a -1b:** Among participants assigned to the intervention group, we will summarize both the number of deprescribing *recommendations* and the number of actual medication *changes* at hospital and SNF discharge and 90-days following SNF discharge. The effect of the intervention on the total number of medications, PIMs, and medications associated with geriatric syndromes at hospital discharge, SNF discharge, and 90-days following SNF discharge will be assessed using mixed effects Poisson regression, allowing for overdispersion (more or less variability than is expected under the Poisson regression model), and adjusting for measurement time point (as a categorical covariate) and the total number of medications at enrollment and the interaction of intervention and time point. The heterogeneity in outcome measures across participants will be modeled using a random intercept term, indexed by subject. Heterogeneity among VA providers and SNFs in the effectiveness of intervention will be modeled using a random intervention effect, indexed by VA provider and SNF. The overall intervention effect will be evaluated using a Wald-type multiple degree-of-freedom test against the null hypothesis of no effect at any time point. The intervention effect at each time point will be summarized using a Wald-type 95% confidence interval. Model fit will be assessed by examining the associated Pearson residuals and other graphical methods. Alternative regression techniques may be used in the case of poor fit, for example, negative-binomial regression. A secondary analysis to explore the possibility of intervention effect modification by hospital length of stay (e.g., longer stay may result in more deprescribing) will be implemented by considering the interaction of hospital length of stay with intervention.

**Hypothesis 1c:** The effect of intervention on the anticholinergic and sedative drug burden index scores at hospital discharge, SNF discharge, and 90-days following SNF discharge will be assessed using linear mixed effects

regression, adjusting for measurement time point, its interaction with intervention and using random effects, testing and summary methods as described for Hypotheses 1a, 1b and 1d. Model fit will be assessed using residual diagnostics and graphical methods. Due to the constrained nature of the DBI values, a ‘beta’ regression method may be required, which is suitable for scores that often occur at a boundary.

**Hypothesis 2a:** Medication adherence will be measured using the ARMS based on an ordinal scale. Functional health status will be measured using the VES-13 total score, also an ordinal outcome. Patient attitudes toward deprescribing (PATD) also will be measured on an ordinal scale. The effects of intervention on these outcomes will be assessed at 7 (except PATD) and 90-days following SNF discharge using mixed-effects logistic regression or proportional odds logistic regression similar to analyses for Hypothesis 2b.

**Hypothesis 2b:** The prevalence and severity of geriatric syndromes will be analyzed at baseline, 7 and 90 days following SNF discharge. The effects of intervention on the prevalence of each type of geriatric syndrome will be assessed using mixed-effects logistic regression, adjusting for measurement time point (categorical) and its interaction with intervention. The severity of each geriatric syndrome is measured on an ordinal scale. Thus, severity will be analyzed using mixed-effects proportional odds logistic regression, also adjusting for measurement time point and its interaction with intervention. For either method random effects, testing, summary and diagnostic methods will be used as described for Hypotheses 1a, 1b and 1d.

**Hypotheses 3a-c:** Descriptive analyses will be performed to examine implementation outcomes: anticipated barriers and facilitators, medication changes per patient following hospitalization, and staff time required for each intervention component. Unanticipated barriers and facilitators and stakeholder input responses will be analyzed using qualitative methods. A research assistant will generate clean versions of the data collection notes. We will code notes using NVivo11® software based on a two-pronged approach that relies on: a) a priori factors, and b) emergent themes or “grounded theory”, an inductive approach in which the categories used for the analysis are derived from the data. The a priori factors include the categories of anticipated barriers and facilitators as well as constructs from CFIR. Analyses will then compare all cases to identify the range among and differences between respondents. Themes will be noted, counted, and documented by illustrative quotations from the notes. Data collection will continue until saturation of themes are reached, likely requiring 20-25 respondents. Ten percent of the notes will be double coded (first by PI then by the study coordinator) to calculate a reliability statistic.]

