## **Post-Intervention Follow-Up**

The intervention ends at hospital discharge. Originally, if the Veteran discharged to any location other than SNF, they were discontinued from study. Due to retention concerns, the IRB approved the retention of Veterans who discharged home (beginning in March 2021).

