### **Repeated Measures**

Barring study withdrawal or death (or hospice transfer), each participant will be assessed at multiple time points. Participants may be clustered by VA provider and/or SNF discharge location. Thus, outcome measurements may exhibit heterogeneity across participants and clusters. Our statistical plan takes full advantage of this information by using a mixed-effects framework for each analysis. In the event that a mixed-effects technique cannot be implemented, an alternative method will be used, and the standard errors of effect estimates will be adjusted using the robust Huber-White ‘sandwich’ method.

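### The primary models give VA providers and SNFs a random intervention effect but name no random intercept, so the standard error of the intervention effect can be wrong in either direction and depends on an unstated treatment coding.

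*Combined protocol and SAP*

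**What the plan says.** Statistical Considerations, Outcomes (Hypotheses 1a-1b) gives each random effect a separate job. For participants: "The heterogeneity in outcome measures across participants will be modeled using a random intercept term, indexed by subject". For clusters, differences between VA providers and SNFs in how well the intervention works "will be modeled using a random intervention effect, indexed by VA provider and SNF". No term is named for providers or SNFs whose patients have more or fewer medications whichever arm they are in.

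The same section carries these random effects to Hypothesis 1c and, explicitly, to 2b. Hypothesis 2a is to be analysed in a similar way to 2b.

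Repeated Measures recognises the missing source of variation: "Participants may be clustered by VA provider and/or SNF discharge location. Thus, outcome measurements may exhibit heterogeneity across participants and clusters". It then says: "Our statistical plan takes full advantage of this information by using a mixed-effects framework for each analysis". It names no cluster term. Neither section gives the treatment coding, the intercept-slope covariance, an ICC or the number of providers.

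**The concern.** A random slope without its intercept is an unusual model. With 0/1 coding it treats control Veterans who share a provider or SNF as independent and lets only intervention Veterans be correlated. If clusters differ in prescribing level, the only cluster term that can take up the difference is the intervention effect. Randomization is not described as stratified by provider or SNF, so the design does not remove the problem.

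Two results are at stake: the Wald tests and intervals for the intervention effect in the primary models, and any reading of how that effect varies across providers and SNFs, which is the stated purpose of the term.

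**Working it through.** **Inputs from the documents.** N = 260, randomized 1:1, so 130 per arm (Sample Size and Randomization). K = 21 SNFs, from the York campus plus 20 contract homes (Study Setting). That section lists only the most common destinations, so K = 40 is also shown. Medication count SD 5.3 (Preliminary Data).

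**Assumed.** ICC ρ from 0.01 to 0.20, two-sided alpha 0.05, total variance 1. The formulas take equal clusters and one measure per Veteran.

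**Step 1: the plan's own figure.** The power above 93% cannot be reproduced, because no effect size, alpha, SD, ICC or attrition accompanies it. On the assumptions above, 93% power corresponds to d = (1.96 + 1.476) × √(2/130) = 3.436 × 0.1240 = 0.426, or 0.426 × 5.3 = 2.26 medications. This serves only as a yardstick.

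**Step 2: clusters differ only in level, 0/1 coding.**
- Cluster intercept model: Var ≈ 4(1−ρ)/N.
- Slope-only model: Var ≈ 4(1−ρ)/N + ρ/K.

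At ρ = 0.05 and K = 21: √0.01462 = 0.1209 against √(0.01462 + 0.00238) = 0.1304. The table gives the ratio of standard errors, slope-only to cluster intercept.

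| ρ | K = 21 | K = 40 |
|---|---|---|
| 0.01 | 1.016 | 1.008 |
| 0.05 | 1.078 | 1.042 |
| 0.10 | 1.159 | 1.087 |
| 0.20 | 1.332 | 1.186 |

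Simulated REML fits agree closely: +4%, +8%, +16% and +33% for K = 21, and +3%, +5%, +9% and +19% for K = 40. With a true intercept variance of 0.10 and a true slope variance of 0, the slope-only model reported a slope variance of 0.093. In 700 trials at ρ = 0.10, its mean standard error was 0.139 against an actual sampling SD of 0.126, and type I error was 3.1%. A Poisson mixed-model check at ρ = 0.10 gave 0.0459 against 0.0409 (+12%).

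**Step 3: against intercept plus slope, the model recommended here.** This model itself costs some precision, so the gap narrows. At ρ = 0.10 its mean standard error was 0.126 to 0.128, so the ratio is 0.139/0.128 = 1.09 to 0.139/0.126 = 1.10. Other runs with 21 unequal clusters gave 1.05 to 1.06 at ρ = 0.05 and 1.11 to 1.17 at ρ = 0.10. With 40 clusters the excess was 4% and 8%; at ρ = 0.02 it was 2%.

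**Step 4: high-count clusters respond more.** Take the extreme case in which each cluster's slope is minus its intercept, both with variance τ². Cluster differences then exist only in the control arm, where the slope-only model has no term for them.
- True Var ≈ 4(1−τ²)/N + τ²/K.
- Variance as the model sees it ≈ [1 + (1−τ²)]/130.

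For τ² = 0.10 the standard errors are 0.1209 (model) and 0.1364 (true), ratio 0.89. For τ² = 0.20 they are 0.1177 and 0.1478, ratio 0.80. Simulation (700 trials each) gave 0.88 and 0.79, with type I error 8.7% and 13.0%. With real slope variation (SD 0.3) and no intercept variation, the ratio was 0.96, about right.

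**Step 5: coding.** With slope-only and ±1/2 coding, the standard error stayed near 0.130 at every ρ from 0.01 to 0.20. In the Step 4 settings it was well calibrated (ratios 0.996 and 1.006). The same data and the same verbal specification therefore give different inference according to a coding choice that the plan leaves open.

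**The case against.** - **Unstated is not excluded.** A reader might infer that the plan rules out a cluster intercept. It does not: Repeated Measures speaks of outcome heterogeneity across clusters, which is what an intercept represents. This stands, and the defect is an incomplete specification. But an analyst who follows the Outcomes text literally would leave the intercept out.
- **Standard errors are not generally too large.** A reader might infer that the plan is merely conservative. Step 4 shows the reverse can happen, and Step 5 that the coding matters.
- **The size rests on assumptions.** The documents give no ICC, and Veterans may go to any SNF. The count models adjust for medications at enrollment, which should absorb some level differences; the simulations omit this, and mostly omit repeated measures and the Poisson scale. A definite loss of power from 93% cannot be claimed, because that figure cannot be reproduced.
- **Spurious heterogeneity.** One simulation found significant slope variance in 28% and 49% of trials at ICC 0.05 and 0.10. That used a likelihood-ratio test that the plan does not specify, so these are not error rates of a planned analysis.
- **Existing safeguards.** Residual checks and alternative regressions are planned, but the example given is a change of distribution, not of random effects. The sandwich fallback applies only when a mixed model cannot be implemented, and a slope-only model may fit without trouble.
- **Veterans sent home.** A reader might infer that they enter the SNF term without a SNF. Post-Intervention Follow-Up does say "the IRB approved the retention of Veterans who discharged home", but Randomization, Intent-to-Treat, & Safety Outcomes restricts analyses to those discharged to SNF. The conflict concerns the analysis population and must be settled first.

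**Conclusion.** The point holds as a gap in the specification of the primary models, inherited by 1c, 2b and 2a. As written, level differences between clusters pass into the intervention-effect variance, and the standard error may err either way. Under 0/1 coding, level-only differences and 21 clusters, the excess is roughly 5% at ICC 0.05 and 10 to 15% at ICC 0.10 relative to intercept plus slope, and smaller with a lower ICC or more clusters. Under perfect negative correlation between intercept and intervention effect, the standard error is 12 to 21% too small. That correlation is an extreme chosen to show direction, not an estimate for this trial.

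The intercept-plus-slope model was run in only 100 to 150 trials per setting, with type I error of about 5 to 7%. At 100 trials the Monte Carlo error is √(0.05 × 0.95/100) = 2.2 percentage points, so those runs do not establish exact calibration. The case for the intercepts rests on the structure of the model.

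**What to change.** In Outcomes, add random intercepts for VA provider and for SNF alongside the random intervention effects, allow intercept and slope to covary, and state the treatment coding. Give an order of simplification if the model does not converge, for example dropping the covariance, then the slopes, and the intercepts last. That order is a modelling preference; what matters is that it is fixed in advance. Carry the change to 1c, 2a and 2b.

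State whether the SNF term applies at hospital discharge, which precedes any SNF care. The destination SNF can index those records, but the plan should say whether a constant SNF effect is meant. Before defining the term for Veterans sent home, reconcile Study Population and Sample Size and Post-Intervention Follow-Up, which retain them, with Randomization, Intent-to-Treat, & Safety Outcomes, which leaves them out.

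The cost is a few sentences and two more random terms with their covariances. The downside is a slightly higher risk of non-convergence, for which Repeated Measures already has a fallback.

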Although most studies have been conducted in non-VA hospital settings, two studies reveal similar rates of polypharmacy and prescribing problems among VA patients. Most recently, a large study involving 462,405 Veterans aged 65 and older examined prescribing quality using VA pharmacy data. Results showed that Veterans were prescribed a median of five medications, and 50% were identified as having one or more types of ‘prescribing problems’ as defined by the following categories: inappropriately high dose (12%), drug-drug interactions (30%), drug-disease interactions (3%), potentially inappropriate per the Beers list (26%) or other high-risk drugs (26%, e.g., warfarin, insulin, and/or digoxin). This study also showed that the total number of medications was the strongest predictor of each type of prescribing problem. Similarly, an earlier study with 196 community-dwelling Veterans aged 65 and older prescribed 5 or more medications showed that 65% were taking one or more medications deemed clinically inappropriate and 57% were taking at least one medication deemed ineffective, not indicated or duplicative. Most importantly, however, the frequency of inappropriate medications increased as the total number of medications increased from a mean of 0.4 per Veteran among those taking five to six medications, to 1.1/Veteran among those taking seven to nine medications, and 1.9/Veteran among those taking 10 or more medications (i.e., hyper-polypharmacy). Underuse also occurred but was much less common, especially for those taking more than eight medications.

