## Primary Outcomes – Medications

Total number of medications: Data collection begins with the Veteran's Essential Medication Review List (EMLR). After this list is abstracted from the medical record, a study NP or PharmD pulled the Controlled Substance Monitoring Database report, called non-VA pharmacies for recently filled prescriptions, reviewed non-VA medical records (i.e., outside hospital or SNF records), and interviewed the Veteran or their surrogate. We included all medications, either prescription or over-the-counter (OTC) that were administered by the following routes: oral, intravenous, intramuscular, sublingual, or ophthalmologic. Veterans (or their surrogate) were given specific prompts if they reported no OTC usage, for example, asking them if they take anything for constipation or allergies. If a patient was admitted from an institutional setting (e.g., outside hospital, SNF, ALF), we request a copy of the medication administration record from the previous 30 days. Medications are considered current/active if the Veteran took it within 30 days of hospitalization. The hospital discharge and SNF discharge medication lists, serve as the outcome data for those respective time points. During the follow-up calls, the study NP or PharmD systematically asked the Veteran for the status of each medication on the enrollment list and discharge lists to determine if and how they are taking it. Afterwards the study clinician prompted the Veteran for any new medications they may be taking.

Potentially Inappropriate Medications (PIMs): We used previously published and validated lists including the Beers criteria, the STOPP criteria, and the RASP list, which have a large degree of overlap. The total number of PIMs is the sum of medications that are found on these lists.

Drug Burden Index (DBI): This score is calculated separately for anticholinergic and sedative medications, which have been linked to functional impairment, falls, and delirium. The DBI is the sum of each individual anticholinergic/sedative medication's prescribed daily dose divided by the sum of the minimum effective dose (per the FDA minimum recommended dose) and the patient's daily dose. The DBI is calculated for all medications including OTCs. We will calculate the DBI at each timepoint, and this will capture dose reductions even when the total number of medications is not reduced.

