## **STATISTICAL CONSIDERATIONS**

### **Sample Size and Randomization**

Existing data indicate that approximately 600 to 700 hospitalized Veterans are referred to SNF annually. Thus, we conservatively estimate that 40% (or, 240 per year) will provide consent, complete baseline assessments and discharge to SNF to yield a total consented sample of 540 across all study months. During the SNF stay, we anticipate ~5% will die, which will leave 513 (or ~256 per group) discharged from SNF. Based on preliminary data, ~15% of patients die within 90 days of SNF discharge. Thus, ~85% (or 393 total) will be alive at 90 days. In addition, we estimate we will be unable to reach ~10%, which will leave ~354 total participants (~177/group) for 90-day follow-up. The population and sample size were adjusted mid-study due to the significant enrollment and retention challenges caused by the COVID-19 pandemic.

It was determined that a sample of 260 Veterans was sufficient to provide power greater than 93% for both the primary and secondary outcomes. Finally, the study enrollment was continued for an additional 10 months beyond the original project timeline.

Participants will be randomized in a 1:1 ratio using permuted blocks of two or four, where the size for each block is selected uniformly at random. This type of randomization ensures balance across the intervention and control groups after every second or fourth randomization (depending on the size of the current block). This randomization scheme will be generated by computer using the Mersenne-Twister pseudo random number.

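### The drug burden models leave out baseline DBI, and the PIM and syndrome-drug models leave out their own enrolment counts, so precision that costs no new data is lost, mainly for DBI

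*Combined protocol and SAP*

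**What the plan says.** The Outcomes section uses one mixed-effects Poisson model for three counts: total medications, PIMs and medications associated with geriatric syndromes. Its covariates are time point, "the total number of medications at enrollment and the interaction of intervention and time point". Total medications at enrolment is the outcome's own baseline for the first count, but not for the other two.

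Hypothesis 1c has a separate linear mixed model for the two DBI scores at hospital discharge, SNF discharge and 90 days, "adjusting for measurement time point, its interaction with intervention and using random effects, testing and summary methods as described" for Hypotheses 1a, 1b and 1d. The cross-reference brings in random effects, testing and summary methods. It names no covariate, and enrolment is not one of the modelled time points. Between-provider and between-SNF variation is "modeled using a random intervention effect, indexed by VA provider and SNF". If the linear model fits badly, beta regression may replace it, "which is suitable for scores that often occur at a boundary".

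The baselines exist. The Schedule of Assessments marks DBI and PIMs under the baseline hospital column, and syndrome-drug counts can be derived from the enrolment list. On DBI, Primary Outcomes – Medications says: "We will calculate the DBI at each timepoint, and this will capture dose reductions even when the total number of medications is not reduced".

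**The concern.** The Study Design section frames the primary outcomes as change, yet the DBI model contains no starting value. The subject random intercept does not replace one, because it is estimated from post-enrolment scores only. The omission does not look like a rule of the plan: the total-medication model adjusts for its own baseline, and Hypothesis 2b includes baseline as an analysed time point.

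Total medications would be a poor stand-in for baseline DBI even if it were carried over, since DBI is meant to register dose reductions that leave the count unchanged. For PIMs, total medications is a partial stand-in. The background section reports that "the total number of medications was the strongest predictor of each type of prescribing problem", and that inappropriate drugs rose "from a mean of 0.4 per Veteran among those taking five to six medications" to 1.1 at seven to nine and 1.9 at ten or more. The count outcomes are therefore the lesser point.

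Precision matters here. The target was cut from 540 to 260, and the claim that "a sample of 260 Veterans was sufficient to provide power greater than 93% for both the primary and secondary outcomes" comes without an effect size, SD, test level or correlation, so spare power cannot be taken for granted.

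**Working it through.** **The plan's power figure.** It cannot be reproduced, because its inputs are not given. Solving backwards with 130 per arm and two-sided 5% (assumed from the 95% interval), 93% power corresponds to a standardised difference d = (1.960 + 1.476) × √(2/130) = 0.426.

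**Validity.** In 4,000 simulated null trials with 130 per arm and baseline correlation r = 0.6, type I error was 4.7% unadjusted and 4.6% adjusted. Both mean estimates were about 0. The SD of the estimate fell from 0.125 to 0.098. The omission costs precision and adds no bias.

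**DBI, linear model, one time point.** The standard error is multiplied by √(1 − r²). Equivalent unadjusted sample = 260/(1 − r²). Power = Φ(d√(n/2)/√(1 − r²) − 1.96). The correlations are assumed, and 130 per arm is a best case.

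| | Unadjusted | r = 0.3 | r = 0.5 | r = 0.7 |
|---|---|---|---|---|
| SE factor | 1 | 0.954 | 0.866 | 0.714 |
| Equivalent N | 260 | 286 | 347 | 510 |
| Power, n = 130, d = 0.426 | 93% | 95% | 98% | 99.8% |
| Power, n = 130, d = 0.30 (assumed) | 68% | 72% | 80% | 92% |
| Power, n = 85, d = 0.426 | 79% | 83% | 89% | 97% |
| Power, n = 94, d = 0.426 | 83% | 87% | 92% | 98% |

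The last two rows apply only if the 93% refers to 130 per arm before attrition. The 85 follows from the retention planned under Sample Size and Randomization: 130 × 354/540 = 85. That chain seems to take the 10% loss twice: 513 × 0.85 = 436, not 393, while 513 × 0.85 × 0.90 = 392. Taking it once gives 130 × 392/540 = 94.

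**How plausible is r = 0.7?** Doubtful. The enrolment list covers the 30 days before hospitalisation. Preliminary Data reports that 1.0 of 2.5 discharge PIMs were newly prescribed in hospital, and that only 6.1 of the 12.6 drugs deprescribed in the pilot were pre-hospital.

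**Random intervention effect.** The covariate does not shrink this component. With 21 SNFs (the York campus plus 20 contract homes, Study Setting) treated as equal in size, variance = (2/130)(1 − r²) + τ²/21. At an assumed τ = 0.2, the SE ratios are 0.959, 0.882 and 0.751, so the cuts become 4, 12 and 25%.

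**PIM count, total medications already in the model.** The basis is 1,500 simulated trials of 260 at one follow-up, analysed by Poisson regression with robust SE. Inputs: rate ratio 0.75; mean PIMs 2.0 at baseline and 2.5 at follow-up; log-normal PIM frailty with SD s; non-PIM count with mean 10 and log-normal SD 0.35; at least 5 medications in total. Only the 2.5 and the minimum of 5 come from the documents. The table shows the SE cut from adding the enrolment PIM count.

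| Correlation of PIM and non-PIM propensity | s = 0.5 | s = 0.7 | s = 0.9 |
|---|---|---|---|
| 0 | 6% | 15% | 25% |
| 0.5 | 3% | 9% | 17% |
| 0.9 | 1% | 3% | 6% |

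The background gradient is 1.9/0.4 = 4.75-fold. Settings that give a ratio of 4.6 to 4.7 have cuts of 1, 7 and 14% at s = 0.7, 0.8 and 0.9. The match is rough, because those data come from community-dwelling Veterans and other criteria. In these simulations, 17 to 29% of Veterans had no PIM at enrolment. Syndrome-drug counts were not simulated; a similar range is assumed.

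**The case against.** The strongest reply is that this is a preference about efficiency, not an error. On the only anchor in the documents, the 93%, the gain is 2 to 7 percentage points; the larger gains need an assumed d = 0.30 or the doubtful r = 0.7. That is fair, and it is why the point is graded as lost precision.

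- **Wording.** Hypothesis 1c is abbreviated, and change as the primary outcome could imply that baseline enters the response. But the section models scores at each time point. Even if total medications were read into the cross-reference, baseline DBI would still be absent. If change scores were intended, their variance is 2(1 − r) against 1 − r² with adjustment: 0.60 against 0.51 at r = 0.7, an 8% SE cut in place of 29%. At r = 0.3 it is 1.40 against 0.91, so adjustment would still be better.
- **Retention.** The 85 per arm rests on a chain that appears to count a loss twice, and on the SNF-only cohort before Veterans discharged home were retained. This stands; 94 per arm is shown beside it, and the fix is the same.
- **Planned test.** The figures are for one time point, while the overall test spans three. Under compound symmetry and a constant effect, neither of which is documented, the information ratio for that test is (1 + 2r)/[(1 − r)(1 + 3r)] = 1.20, 1.60 and 2.58, against 1.10, 1.33 and 1.96 at one time point. The √(1 − r²) factor does not carry over to beta regression.
- **Timing of the list.** The study NP or PharmD who verifies the enrolment list also delivers the intervention, and nothing says that verification ends before randomisation. This stands as a condition. It applies equally to the enrolment covariate already in the plan.

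**Conclusion.** The concern holds. Baseline DBI is missing from the Hypothesis 1c models, and the PIM and syndrome-drug models lack their own enrolment counts, although all of these values are collected or derivable. The planned contrasts remain valid under randomisation as far as the covariate choice goes.

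For DBI, a reasonable reading is an SE cut of about 5 to 13% (r = 0.3 to 0.5), or 4 to 12% with the assumed random SNF effect. The 29% at r = 0.7 is an upper case that the pilot and preliminary data make doubtful. For PIMs the cut is smaller and depends on how closely total medications tracks the PIM count. All of these sizes rest on assumed correlations. The change is worth making because DBI is a primary outcome and the adjustment needs no new data; the count outcomes alone would merit a lower priority.

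**What to change.** In the Outcomes section, add enrolment anticholinergic DBI, sedative DBI, PIM count and syndrome-associated-drug count, each to the model for its own outcome. Keep total medications at enrolment in the count models. Enter the counts in a form that allows zero, such as log(count + 1), because eligibility guarantees at least 5 medications but not at least one PIM. If beta regression or another nonlinear model replaces the linear DBI model, report the effect as conditional on baseline. State that the enrolment list is fixed before allocation, or describe how it is protected from knowledge of allocation.

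The cost is SAP wording, with no new data. Since Study Design puts final follow-up in March 2023, the change must be dated and fixed before any unblinded analysis.
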